PhilPEN was initially (2013) supported by DOH central procurement and distribution of drugs to RHUs under the Complete Treatment Packs (COMPACKs) program. In 2015, support for PhilPEN was shifted to the Maintenance Medicines Program and the Hypertension and Diabetes Clubs (H and D). Instead of the seven molecules for CVDs supplied under the COMPACK program, only four molecules are provided by the latter programs. Specifically, these programs are intended to make the anti-hypertensives (amlodipine, losartan, and metoprolol), as well as one diabetes medication (metformin), available at all RHU/CHCs at no charge irrespective of the patient's insurance cover or income. Statins are not supplied, despite the protocol stipulating that they should be given to all patients with a CVD risk in excess of 30% and to those with particularly high total cholesterol (≥ 8 mmol).

Allocation of the drug supply across facilities is demand based, although interviews conducted by the study team in selected RHUs reveal substantial delays in deliveries and possible stock-outs. There is substantial variation across facilities in the management of drug inventories. Some allow for potential shortages by admitting patients to the program only if a six-month supply of medication is secured in advance for that patient.

The study will be conducted in Nueva Ecija, a landlocked province of 2.15 million people in Central Luzon, which is one of the regions with the highest prevalence of major CVD risk factors, such as high blood glucose and smoking, in the country (FNRI-DOST, 2015). The province of Nueva Ecija is chosen because of its relatively high rate of poverty (29.6% compared with national average of 26.3% in 2015) despite being reasonably accessible from Metro Manilla (180 km). A high prevalence of poverty is important since the study aims to induce utilization of preventive care at RHU/CHCs, which mainly serve the poorer population. The vast majority of the population (83%) is rural dwelling.

3. Research objectives, questions and hypotheses

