[H3d] Updating of beliefs is asymmetrical in response to positive information, i.e. $prior_i > predicted_i$, and negative information i.e. $prior_i < predicted_i$.

Test:

• We run the following regression:

$$\begin{array}{l} (posterior_{i} - prior_{i}) = \lambda_{1i}(predicted_{i} - prior_{i}) \times 1(predicted_{i} \leq prior_{i}) + \lambda_{2i}(predicted_{i} - prior_{i}) \times 1(predicted_{i} > prior_{i}) + \varepsilon_{i} \end{array}$$

and test $\lambda_{1i} = \lambda_{2i}$ against $\lambda_{1i} > \lambda_{2i}$. That is, under the alternative hypothesis, individuals who receive good news respond more than those who receive bad news. Such asymmetric updating is

consistent with the reinforcement of optimism bias. However, in light of Harris and Hahn (2011) and Shah et al. (2016), we cannot infer a mechanism for optimism bias from $\lambda_{1i} > \lambda_{2i}$ alone.

Q4: Do beliefs about susceptibility to CVD affect behavior in relation to lifestyles and the demand for preventive care?

[H4a] Beliefs play an important role in determining health behavior. Individuals are forward-looking and take into account their perceived susceptibility to CVD in deciding on their use of primary prevention and health lifestyles. Further, they use perceptions of the response of CVD risk to risk factors when deciding whether to change health habits such as smoking and diet/exercise.

Test:

- Run regressions of the form, y_i = βx_i + θp̂_i + ε_i, where the dependent variable is an indicator of a) whether the person has attended a health facility for a checkup, including blood pressure measurement and diagnostic tests, b) whether is taking medication for hypertension/diabetes, c) smoking (at all and intensity), d) BMI, e) exercise and possibly others. In one set of regressions, p̂_i will be the predicted value of the perceived personal CVD risk, which will be obtained from of one of the regressions described under [H3a]. That is, in the first stage, perceived personal CVD risk measured after the giving the treatment group information on the base rate and their predicted personal risk is regressed on the treatment group indicator. The IV estimate of θ tells us how behaviour responds to changes in CVD risk perceptions induced by information on those risks.

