Individuals may be apprehensive of utilizing their beliefs about CVD risk because they lack confidence in the accuracy of those beliefs. Their beliefs are ambiguous. If individuals are ambiguity seeking in the loss domain, which is often found (Dimmock et al 2015), and are informed that their risks are lower than they had reported, then on gaining confidence in their downwardly revised beliefs they may become responsive to them. Being surer that the CVD risk is 15% rather than being very uncertain that it is 20% may cause an individual to adopt healthier behaviour.

Test:

• Repeat the regressions of the previous test but rather than including a single indicator of treatment group enter two indicators. One identifies respondents in the treatment group informed that their risk is above their initially reported risk. The other identifies respondents in the treatment group informed that their risk is at or below their reported risk. If it is only the correction of bias in risk perceptions that affects behaviour, then only the first group should adopt healthier behaviour. The second group, if anything, should adopt less healthy behaviour. If, to the contrary, the second group responds to the positive news they are given of their CVD risk by adopting healthier habits, this suggests an effect through reduced ambiguity. In addition, we will examine how the provision of information affects stated confidence in individuals' estimates of their risks of heart attack/stroke.

Q6: Is PhilPEN effective in delivering primary prevention of CVD to those who seek care at RHU/CHCs?

[H6a] As currently implemented, PhilPEN does not reduce the risk factor exposure and increase the medication of individuals with elevated CVD risk.

Test:

- Induce random variation in presentation for checkup at RHU/CHCs, which under PhilPEN are required to conduct CVD risk assessment of all patients, to screen those meeting specified criterion, to counsel all those screened on smoking cessation and to provide hypertension and diabetes medication to those at high risk defined by the WHO PEN protocol.
- The information intervention will not be used to generate this random variation since beliefs about CVD risk can impact on behaviour directly even without contact with health facilities and the PhilPEN program.

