- Rather, a *randomized encouragement design* is adopted in which respondents in randomly selected barangays will be offered the opportunity to enter a lottery for a money prize on condition of attending a RHU/CHC for a checkup within a month. The lottery will have a selection probability of 10% and a prize of 5,000 PHP. There will be one lottery within each of the selected barangays.

- The offer of a lottery ticket will be used to instrument presentation for checkup at RHU/CHC allowing the effect of the latter on predicted 10-year CVD risk, plus risk factors (smoking, BMI, blood pressure), hypertension diagnosis and medication at follow-up to be identified.
- Specifically, we will estimate the regression model,

$$Y_{it} = \gamma Y_{it-1} + \beta x_{it-1} + \tau \,\hat{s_i} + \mu_{it} \tag{6.1}$$

where Y_{it} represents the outcome variable (e.g. predicted CVD risk) at follow-up and \hat{s}_i is the predicted value of a binary variable that equals one for those who attended a RHU/CHC for a checkup, and zero otherwise. The prediction is obtained from the first stage regression described in [H6b] that makes use of the random offer of entry to the lottery. Y_{it-1} and x_{it-1} are the outcome and covariates respectively at baseline. Note that only individuals that are either in the lottery incentive group or in the control group are used for this regression.

• The instrumental variable estimate of τ is an estimate of the impact of a RHU/CHC checkup on the outcome for those induced to present for checkup by the lottery offer who would not have presented for a checkup otherwise.

[H6b] The lottery offer is a strong instrument for presentation at a RHU/CHC for a checkup.

Test:

• Using both the treated respondents who are offered the lottery prize and the control respondents who are not, we will regress a binary variable indicating RHU/CHC attendance (s_i) on a binary variable indicating whether or not the lottery prize was offered (L_i) , i.e.

$$s_i = \gamma Y_{it-1} + \beta x_{it-1} + \kappa L_i + u_i.$$
(6.2)

 $\hat{\kappa} > 0$ indicates that the lottery offer raises attendance. We will test for weakness of the instrument.

[H6c] Individuals who have a preference for risk respond more to the offer of a lottery prize. Thus, the intervention has a larger effect on individuals who potentially engage most in lifestyles that bring exposure to CVD risk.

Elaboration

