The lottery instrument will allow identification of a local average treatment effect. That is, the effect of the PhilPEN on those who respond to the offer of the lottery but would not otherwise have presented for a checkup at a RHU/CHC, i.e. *compliers*.

Risk averse individuals are most likely to invest in preventive care and to present for checkup at a RHU/CHC in the absence of any lottery incentive. They are most likely to be *always takers*. This can be established assuming an expected utility maximizer who decides whether to invest in preventive care by comparing its benefit – reduced probability of succumbing to CVD – with its cost, which includes fees, transport expenses and foregone earnings.

While the lottery will be offered without charge to all participants in the treatment group, its conditionality on going for a checkup at a RHU/CHC means that taking up the offer carries a cost. Hence,

the lottery is a gamble and will appeal most to individuals with a preference for risk. These are the individuals who are least likely to go for a checkup in the absence of the lottery incentive. Hence, we expect compliance to be greatest for those with a preference for risk, who may be more likely to engage in unhealthy behaviour.

The hypothesis that compliance will be greatest among those with a preference for risk is founded on the logic of the expected utility model in which risk attitudes are entirely captured by concavity of utility. Alternative models can give different predictions. For example, if one allows for nonlinear weighting of probabilities, then individuals who overweight small probabilities will find the lottery most attractive. This is the reason we believe a lottery offers a more efficient mechanism for incentivizing checkup than the offer of a subsidy to everyone. However, in that case, individuals who are excited most by the lottery may also be worried most by reasonably small CVD risks and may be most likely to have invested in preventive care without the lottery incentive.

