The information intervention may impact on this outcome through multiple mechanisms. Individuals who are made aware that the CVD risk for individuals with their risk factor profile is higher than they had anticipated, who are provoked to recognize that they face a non-negligible risk without having given serious thought to this risk previously and who are told by how much the risk could be reduced by quitting smoking, reducing blood pressure, losing weight etc, may be provoked to take actions to reduce their risk. Actions could include: going for a checkup at a RHU/CHC or other health facility with the possibility of subsequently being put on medication for hypertension, diabetes or high cholesterol, attempting to lose weight through diet and/or exercise, and quitting smoking. Any efforts that are

effective in reducing blood pressure, reducing weight and stopping smoking will translate into a reduced 10-year CVD risk score.

The lottery intervention may impact on the predicted 10-year CVD risk by inducing respondents to attend a RHU/CHC where they can access PhilPEN risk assessment. Given the age criterion for inclusion in the study (40+), according to the protocol all those attending a RHU/CHC should be subject to PhilPEN risk screening, which includes tests for blood glucose, urine protein and cholesterol, in addition to measures of blood pressure and weight taken in risk assessment. All those screened should be given counselling on smoking cessation, diet and exercise. Those with sufficiently high risk, should be given medication for hypertension and/or diabetes, which are supplied to RHU/CHCs by the department of health. According to the protocol, those with sufficiently high risk should also be given statins, although these are not supplied by the department of health.

The proportion of the population with elevated CVD risk is likely to be more important for population health than is the mean risk. Unfortunately, we do not have data that allow us to estimate the proportion with elevated risk predicted by the Globorisk algorithm. Hence, we cannot conduct power calculations for this outcome. However, we intend to estimate the impact on it providing that an ex-post calculation confirms that there is sufficient power. We will estimate effects on:

ii) Proportion with 10-year CVD risk (Globorisk prediction) $\geq \tau\%$

The threshold (τ) for elevated CVD risk will be set at 10%, and if there proves to be sufficient power, also 20% and 30%.

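### The H6a estimate compares a RHU/CHC checkup with each complier's next-best option, not with no checkup, and the plan does not measure how often that option is another provider

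*Combined protocol and SAP*

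**What the plan says.** Equations (6.1) and (6.2) in Section 3.2 use the lottery offer as an instrument for s, a "binary variable that equals one for those who attended a RHU/CHC for a checkup, and zero otherwise". A checkup at any other facility is coded zero.

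The plan describes the people to whom the estimate applies in two ways. [H6a] calls them "those induced to present for checkup by the lottery offer who would not have presented for a checkup otherwise". The elaboration of [H6c] calls compliers "those who respond to the offer of the lottery but would not otherwise have presented for a checkup at a RHU/CHC". Only the second matches the coding of s. Section 10.2 (Results, last paragraph) is closer to the first: it sets lottery-arm people who attend against control-area people who do not, without saying whether the latter may have been seen elsewhere.

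The plan recognises other providers. Section 7 (Principal outcome), on the information arm, mentions "going for a checkup at a RHU/CHC or other health facility". [H4a] has as an outcome "whether the person has attended a health facility for a checkup, including blood pressure measurement and diagnostic tests". Neither is carried into the lottery analysis. The compliance paragraph of Section 10.1 allows for control respondents who attend a RHU/CHC unprompted, but not for checkups elsewhere.

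**The concern.** H6a is stated as an absence of effect: "As currently implemented, PhilPEN does not reduce the risk factor exposure and increase the medication of individuals with elevated CVD risk". A small estimate therefore supports it, and Section 3.1 already names deficient operation of the programme in facilities as a possible explanation. A small estimate could also arise because some compliers exchanged one checkup for another. The planned analyses do not separate these explanations.

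Switching is foreseeable from the plan. Under Section 13, respondents with raised readings are advised to see a physician or, at higher readings, to go to the nearest health facility. The advice does not name the RHU/CHC and is not limited to one arm. The voucher pays only for a visit to a designated RHU/CHC, so it can redirect people who would have acted on that advice elsewhere.

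**Working it through.** **1. The plan's own figure.** Inputs: control mean 11.35 and treated mean 10.89 (Table 5); SD one fifth of the mean, 2.27 (Section 10.1); two-sided 5% (two-sided is assumed) and 80% power; ICC 0.1, cluster size 10, correlation 0.6, compliance 0.6 (Table 4).

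- Design effect: 1 + 9 × 0.1 = 1.9. ANCOVA factor: 1 − 0.36 = 0.64.
- n = 2 × (2.27 × 2.802 / 0.46)² × 1.9 × 0.64 = 464.8, rounded up to 47 clusters of 10, or 470.
- 470 / 0.6² = 1,305.6, which is the 1,306 per arm in Table 6. The sample size calculation reproduces and is not in question.

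**2. What the IV estimate measures.** Let Δ be the effect of a RHU/CHC checkup against no checkup, B the effect of a checkup elsewhere against no checkup, and q the share of compliers who would have had a checkup elsewhere without the offer. Then

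τ = (1 − q)Δ + q(Δ − B) = Δ − qB = Δ(1 − qλ), where λ = B/Δ.

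A simulation of 2 million people, with q of 0, 0.25 and 0.5 and λ of 0, 1 and 2, agreed with this to within 0.005.

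**3. Illustrative size.** The documents give neither q nor λ, so both are assumed. Δ is set to 0.2 SD. Power is Φ(0.6τ√(1,074/2) − 1.96), where 1,074 = 1,306 / (1.9 × 0.64).

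| q | τ, λ = 1 | power | τ, λ = 0.5 | power |
|---|---|---|---|---|
| 0 | 0.20 | 79.4% | 0.20 | 79.4% |
| 10% | 0.18 | 70.6% | 0.19 | 75.2% |
| 20% | 0.16 | 60.4% | 0.18 | 70.6% |
| 30% | 0.14 | 49.5% | 0.17 | 65.7% |

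At the adopted 1,361 per arm (the binary-outcome column of Table 6), power with λ = 1 is 81.0%, 72.4% and 62.2% at q of 0, 10% and 20%.

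**4. The direction is conditional.**

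- Care elsewhere has no effect (λ = 0): τ stays at 0.20 for any q.
- Care elsewhere is much more effective (Δ = 0.2, B = 0.5, q = 0.5): τ = 0.2 − 0.25 = −0.05, so the sign reverses.
- A RHU/CHC checkup does nothing and care elsewhere helps (Δ = 0, B = 0.2, q = 0.3): τ = −0.06, away from zero in the harmful direction.

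**5. q can be estimated.** Let a_R and a_O be the coefficients on the offer for RHU/CHC checkups and for checkups elsewhere. If the offer moves people only towards RHU/CHCs, and those it moves give up the other checkup, q = −a_O / a_R. With hypothetical values a_R = 0.60 and a_O = −0.06, q is 0.10.

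**The case against.** The [H6a] sentence can be read as shorthand. It opens by referring to a RHU/CHC checkup, the lottery can only prompt such a visit, and [H6c] gives the full definition. That stands: this is one loose sentence, echoed in Section 10.2, and not a consistent misreading.

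A reader might infer that the IV estimate is biased towards zero. The documents do not support this. Two-stage least squares is consistent for a RHU/CHC checkup against the next-best option, which is a legitimate question about the programme as implemented. A different comparator is a different estimand, and step 4 shows that shrinkage is not guaranteed.

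A reader might also infer that the trial is underpowered. That does not follow either. Section 10.1 sets 0.2 SD as a generic small effect and does not define it against no checkup. Read as the smallest detectable τ, it loses nothing.

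Switching may be rare. The province was chosen with a view to "utilization of preventive care at RHU/CHCs, which mainly serve the poorer population", and Section 9 excludes people already on antihypertensives and those with diagnosed diabetes or heart disease. Delivery is also not judged on τ alone: Section 5.3 plans to check whether facilities follow the protocol, Section 7 covers advice, counselling, tests and medication, and the point person records what was done. These points limit the likely damage. They do not show how many compliers came from other providers.

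**Conclusion.** The concern holds as a matter of comparator and interpretation. The [H6a] wording promises a contrast with no checkup that the coding of s does not deliver, and no planned analysis shows how far the two differ. The estimator and the sample size stand.

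The difference is qB, and its size cannot be derived from the documents. The illustrative fall from 0.20 to 0.18 or 0.16 SD assumes care elsewhere is as effective as a RHU/CHC checkup and that 10% or 20% of compliers switch. Shrinkage requires care elsewhere to help in the same direction and qλ to be below 1. The point matters because H6a is framed as no effect, so an unmeasured q changes what a weak τ can be taken to show.

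**What to change.** - In [H6a] and the last paragraph of Section 10.2, add the RHU/CHC qualifier already used in [H6c], and state that τ is relative to each complier's next-best option.
- Ensure the follow-up questionnaire records checkups by facility type in both the lottery and control arms. The point person's records cover voucher holders only, so coding s for controls already requires much of this. The item must be in place before the shortened follow-up instrument is final.
- Run (6.2) also with any-facility checkup and with other-facility checkup as the dependent variable. Report the fall in other-facility checkups divided by the RHU/CHC first stage, with its confidence interval, as the estimated share of compliers drawn from other providers. State the assumption that the offer moves people only towards RHU/CHCs. Because RHU/CHCs may themselves refer patients onward (Section 2), identify visits made on such referral. One minus the ratio of the any-facility to the RHU/CHC coefficient is a useful cross-check.
- Interpret a weak τ under H6a in light of that share.
- Do not add an IV model with any checkup as the treatment. The offer would then also act through change of provider, so the exclusion restriction fails unless switching has no effect.

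The cost is one facility-type item, one or two extra regressions and a few sentences of interpretation.

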- The likelihood insensitivity parameter, α_i , and the utility curvature parameter, r_i , will be identified for each individual *i* using their responses to hypothetical lottery (in gain domain) choice questions specifically designed for use in a survey context and previously used in the Philippines to estimate risk preferences (Van Wilgenburg et al., 2017).
- First, we will test whether compliance varies with a composite measure of risk aversion that comprises both utility curvature and likelihood insensitivity. Using r_i and α_i we will compute

each individual's certainty equivalent of the lottery (CE_i) , and subtract this from the expected value of the lottery (EV = 500) to get the risk premium R_i . This is calculated for all individuals irrespective of whether they are in the treatment group offered the lottery. $R_i > 0$ indicates risk aversion, $R_i < 0$ indicates risk loving and $R_i = 0$ is risk neutrality.

• We will estimate the following regression model,

$$s_i = \gamma Y_{it-1} + \beta x_{it-1} + \psi_1 L_i + \psi_2 R_i + \psi_3 L_i \times R_i + u_i.$$
(6.3)

- ψ_1 corresponds to the lottery response of risk neutral individuals.⁴ This will be positive if the expected gain from the lottery (500 PHP) is sufficient to bridge the shortfall of the expected health gain of the checkup from its cost. In the absence of the lottery incentive, this shortfall presumably explains why the individual does not go for a checkup. If the estimate of this parameter is not significantly greater than zero, we will learn that the perceived gains of a checkup fall short of the costs by more than 500 PHP.
- $\psi_3 < 0$ corresponds to greater compliance among more risk loving individuals.
- Because the estimates of the individual specific risk parameters, and so the risk premium, can be expected to be noisy, we will also try an alternative specification that enters binary indicators of whether the respondent is risk loving or risk averse (interacted with the lottery indicator) into the first stage regression, with risk neutral being the reference category.
- After having established whether compliance varies with a composite measure of risk attitudes, we will explore whether response to the incentive varies with utility curvature and likelihood insensitivity separately. We will estimate the following type of regression model,

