10.1 Parameter values

To the extent that it is possible given the estimates available, we have strived to base the choice of parameter values on evidence. However, it must be acknowledged that, as is often the case with power calculations, the evidence is often lacking or meagre, and we often must resort to guesstimates. In doing so, we have endeavoured to err on the side of conservatism and have conducted sensitivity analyses.

Power

Power is set to 80% and statistical significance to 5%.

Minimum detectable effect size

We calculate the sample size necessary to detect a small effect size (δ) defined as 0.2 standard deviation (SD) units (Cohen 1992). Consider our main outcome i) – the 10-year risk of a heart attack or stroke predicted by the office-based Globorisk algorithim. Given an estimated mean 10-year CVD risk of 11.35% in the control group, which we obtain from Globorisk for individuals aged 40-69 with mean values of all risk factors, if the standard deviation is one fifth of the mean, then an effect size of 0.2 SD corresponds to a 4% reduction in the mean. The assumption that the standard deviation is one fifth of the mean is based on estimates of the distribution of 10-year CVD risk scores (Gale et al 2014; Gray et al 2014). However, we caution that these estimates are not obtained using the Globorisk algorithm and most are for samples of high-income country populations.⁷

We deliberately choose a small effect size in order to ensure that our samples will be sufficient to detect only marginal impacts of the interventions on the risk factors that determine the CVD risk prediction. The logic is threefold. First, risk factors such as smoking and weight are notoriously hard to influence. Second, our information intervention is of unknown effectiveness and we recognize a possibility that a non-negligible fraction of respondents are unable to absorb the information provided on their CVD risks. Third, while the procedures defined by the PhilPEN protocol are proven to be effective, our aim is to establish effectiveness as the program is implemented, which may fall well short of the stipulated testing, medication and counselling.

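### H6c turns a non-significant lottery response among risk-neutral people into a positive finding of a shortfall above 500 PHP

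*Combined protocol and SAP*

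**What the plan says.** **H6c.** Model (6.3) in section 3.2 regresses attendance at the health facility on the lottery offer L, the risk premium R and their product. The plan interprets ψ1, the coefficient on L, as the response of risk-neutral people (R = 0). It then fixes the reading of a null result: "If the estimate of this parameter is not significantly greater than zero", the conclusion is that "we will learn that the perceived gains of a checkup fall short of the costs by more than 500 PHP". It gives no interval, margin or power for ψ1. The next points in the same list expect the individual risk premiums to be noisy and add a specification that groups people as risk loving or risk averse, with risk neutral as the reference.

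**H6a.** The policy hypothesis is worded as an absence of effect: "As currently implemented, PhilPEN does not reduce the risk factor exposure and increase the medication of individuals with elevated CVD risk". The coefficient τ in (6.1) "is an estimate of the impact of a RHU/CHC checkup on the outcome for those induced to present for checkup by the lottery offer". No rule says how a non-significant τ is to be read.

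**The concern.** The H6c sentence makes a positive, quantified statement about costs and benefits out of a failure to reject zero. There are two separate faults.

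- **Statistical.** Non-significance does not show that the response is zero. The interval may include a response that matters.
- **Logical.** Even a precisely estimated zero would not establish the shortfall. ψ1 is in effect the share of risk-neutral people whose shortfall lies between 0 and 500 PHP. That share is small if nearly everyone's shortfall exceeds 500 PHP, but also if nearly everyone has no shortfall and attends anyway. The plan itself recognises always-takers (H6c, elaboration) and expects some controls to attend without inducement (section 10.1, compliance rate).

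At stake is a published explanation of why people do not attend that the data may not support. H6a carries a milder form of the same risk, because an ordinary test can reject a no-effect statement but cannot confirm it.

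**Working it through.** **1. The plan's sample size reproduces.** Inputs from section 10.1 and Tables 4 and 5: "Given an estimated mean 10-year CVD risk of 11.35% in the control group"; treatment-group mean 10.89; SD one fifth of the control mean, 11.35/5 = 2.27; 5% significance (two-sided reproduces the figure) and 80% power; ICC 0.1; 10 per cluster; correlation 0.6; compliance 0.6.

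- Difference 0.46, SD 2.27: 383 per arm before adjustment.
- Design effect 1 + 9 × 0.1 = 1.9; ANCOVA factor 1 − 0.36 = 0.64; 383 × 1.9 × 0.64 = 465.7.
- Rounded up to 47 clusters of 10 = 470; 470/0.6² = 1,305.6. Table 6 states 1,306.
- The binary-outcome size the plan adopts matches 49 clusters: 490/0.36 = 1,361.

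**2. Precision of ψ1, full-sample approximation.** The plan gives neither control attendance nor an ICC for attendance. Assume the largest binary variance (0.25) and the design effect of 1.9:

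- SE = √(2 × 0.25 × 1.9/1,361) = 0.026.
- Just non-significant estimate: 1.96 × 0.0264 = 0.052, about 5 points. Its 95% interval reaches 2 × 0.052 = 0.104, about 10 points.
- This is not an upper bound. ψ1 is the effect at R = 0 in an interaction model, so its SE grows by √(1 + q²), where q is the distance of mean R from zero in SDs. At q = 1 the factor is 1.41, the SE about 0.037, and the interval reaches about 15 points.

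**3. Precision when risk-neutral people are a separate group.** In the alternative specification the lottery coefficient rests on that group alone. Its share and its control attendance are not given, so both are assumed. SE = √(2p(1 − p)/n), with about one such person or fewer per cluster, so no clustering penalty. Two-sided power for a true 10-point rise in attendance:

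| Risk-neutral share | n per arm | p = 10% | p = 20% | p = 30% |
|---|---|---|---|---|
| 10% | 136 | 79% | 54% | 44% |
| 5% | 68 | 49% | 31% | 25% |

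**4. The logical fault needs no sampling error.** ψ1 cannot exceed 1 minus the attendance that risk-neutral people would show without the lottery. The closer that attendance is to 100%, the closer ψ1 is to zero, with no shortfall anywhere. Error in R also pulls ψ1 towards the average response, so it is not purely the response of risk-neutral people.

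**5. Precision of τ, full sample.** Taking 0.6 as the between-arm difference in attendance:

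- SE = √(2 × 1.9 × 0.64/1,361)/0.6 = 0.0423/0.6 = 0.070 SD; 95% half-width 0.138 SD.
- A just non-significant estimate has an interval reaching 0.276 SD, or 0.276 × 2.27 = 0.63 risk points, 5.5% of the mean. The plan's target is smaller: "an effect size of 0.2 SD corresponds to a 4% reduction in the mean".
- Chance of non-significance: 71% at a true 0.10 SD, 43% at 0.15, 19% at 0.20.
- At 50% compliance, the plan's sensitivity value, power at 0.2 SD is about 66%.
- H6a names people with elevated risk, a share that section 7 says cannot be estimated in advance. If it is 50%, 30% or 20% (assumed), power at 0.2 SD in that group is about 65%, 50% or 39%.

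**The case against.** **On H6c.** The preceding sentence has in mind a person who would not attend without the lottery, and for that person a lack of response does point to a shortfall above the lottery's expected value. Control attendance is in the data, so a high attend-anyway rate would be visible. If the response is anywhere near the assumed 60%, ψ1 will be detected easily, and at an SE of 0.026 a null would limit the response to roughly 10 points or less. This is one interpretive sentence in a mechanism analysis; it touches no principal outcome, estimator or sample size. All of that stands and limits the practical reach. It does not rescue the rule, which is invoked only when the response looks small. ψ1 averages over people who would and would not attend, and the rule does not refer to control attendance.

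**On H6a.** A reader might infer that the plan will treat a non-significant τ as confirming that PhilPEN does not work. The documents do not say so. Q6 is an open question, section 1 asks to what extent the programme succeeds, and τ is presented as an estimate with no accept-or-reject rule. Nor would a real benefit usually be missed: non-significance is the likelier result only below about 0.14 SD, and missing half the design target is ordinary for a trial with 80% power.

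A reader might also want 0.2 SD used as a margin for declaring the programme ineffective. Nothing in the documents gives it that role; it is a minimum detectable effect. At an SE of 0.0705 such a rule would declare ineffectiveness whenever the estimate fell below 0.2 − 0.138 = 0.062, which happens about 29% of the time when the true benefit is 0.10 SD. If the half-width fell below 0.10, one result could exclude both 0 and 0.2 and be labelled effective and ineffective at once.

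**Conclusion.** The H6c sentence is wrong as written, on both statistical and logical grounds, and should be changed. The full-sample SE of about 0.026 rests on maximum binary variance and an assumed attendance ICC of 0.1, and it is larger if mean R is away from zero. On that basis a just non-significant ψ1 leaves a response of about 10 points possible; with few risk-neutral people the separate-group specification would often miss a 10-point response. The always-taker argument does not depend on any of these figures.

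The H6a point is secondary: the hypothesis is worded as no effect and the plan is silent on how to read a null. The figures for τ (SE about 0.070 SD, interval reaching about 0.28 SD) rest on the plan's own parameters and the full sample; precision in the elevated-risk group that H6a names would be lower. The fault is the absence of a stated reading, not a stated misreading, and the sample-size arithmetic is sound.

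**What to change.** **H6c.** Delete the sentence on what a non-significant ψ1 teaches. In its place: report ψ1 with its 95% CI alongside control-arm attendance; if the interval includes zero, say that the data do not show a response among risk-neutral people and give the upper limit as the largest response still compatible with them. Draw no conclusion about the size of any shortfall from non-significance.

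**H6a.** Add that τ will be reported with its 95% CI for each outcome, and that a non-significant τ will not be described as support for H6a.

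**Cost.** A few sentences, with no change to design, data collection, estimators or sample size. The plan gives up the 500 PHP inference from a null ψ1 and any claim of ineffectiveness that rests on non-significance alone.
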